7.3 Cycles 2 and Higher

The following procedures will be performed prior to dosing as noted. Routine clinic visits performed within ± 2 days of the nominal visit day will not be considered protocol deviations.

- Symptom-directed physical examination, weight, and ECOG: Day 1 each cycle starting with C2.
- Vital signs: up to 4 hours pre-dose on Day 1 each cycle starting with C2.
- Resting 12-lead ECG (2 hours [± 10 minutes] post-dose on C2D1, C3D1, C4D1, C5D1 and C6D1 and every 12 weeks thereafter). Additional ECGs may be performed if clinically indicated.
- Blood sample of population PK (2 mL whole blood) for all enrolled subjects: each cycle D1 predose.
- Serum or urine pregnancy test for women of childbearing potential (surgically sterilized females or those who have not experienced menses for at least 2 years are not required to be tested): Day 1 each cycle starting with C2.
- Hematology: (as described in Section 7.1). Day 1 each cycle starting with C2.
 - Note: Patients found to have treatment-emergent hematologic toxicity of Grades 3 or 4 will be monitored at least weekly until resolution.
- Serum chemistries (as described in Appendix H): Day 1 each cycle starting with C2.
 - Note: Patients found to have treatment-emergent laboratory toxicity of Grades 3 or 4 will be monitored at least weekly until resolution.
- LFTs, including AST, ALT, ALP, and total and direct bilirubin: C2D15 and C3D15.
- Thyroid panel: Day 1 of odd-numbered cycles, starting with C3.
- Urinalysis: D1 C2, and as clinically indicated.
- Dispense selpercatinib.
- Selpercatinib administration.
- Outpatient diaries for recording daily selpercatinib dosing, H2 blockers and antacids.
- AEs.
- Concomitant medications.
- Patient-reported outcomes:
 - For MTC patients with diarrhea present at baseline: bowel diary, Day 1 each cycle starting with C2.
 - EORTC QLQ-C30, completed at the same cycle visits as disease assessments until EOT.

The following procedures will be performed as planned even if cycles are delayed. As a result, the following procedures may not always occur at the beginning of a cycle.

- Calcitonin, CEA: for patients with MTC only; Day 1 of C2 and odd-numbered cycles, starting with C3 through C13, and every 12 weeks thereafter (± 7 days of each radiologic disease assessment). For each patient, all tests for calcitonin and CEA should be performed in the same laboratory to minimize intra-patient, lab-to-lab variability in their measurement.
- Thyroglobulin: for patients with non-MTC thyroid cancer only, unless not measurable due to presence of anti-thyroglobulin antibodies): Day 1 of C2 and odd-numbered cycles, starting with C3 through C13, and every 12 weeks thereafter (± 7 days of each radiologic disease assessment). For each patient, all tests for thyroglobulin should be performed in the same laboratory to minimize intra-patient, lab-to-lab variability in their measurement.
- Blood cortisol, ACTH, 24-hour urine for free cortisol: for patients with Cushing's disease related to their cancer. Day 1 of C2 and odd-numbered cycles, starting with C3 through C13, and every 12 weeks thereafter (± 7 days of each radiologic disease assessment). If done, urine collection should begin pre-dose.
- Radiographic disease assessment: every 8 weeks (± 7 days) beginning with C3D1 through C13D1, and every 12 weeks (± 7 days) thereafter until PD, withdrawal of consent, or initiation of a new anticancer therapy(ies), including imaging of the chest, abdomen, and pelvis, utilizing the same modality(ies) as used for the baseline imaging assessment. Additionally, any studies performed at baseline that are positive for sites of disease should be repeated at all post baseline assessments. Additional studies can also be performed as clinically indicated. Please refer to the Imaging Manual for guidelines on how the various imaging studies should be performed.

Notes:

- Patients who discontinue study drug for reasons other than PD (e.g., AE, noncompliance, etc.) may (but, for practical reasons and to minimize patient inconvenience, are not required to) have scans performed and collected as defined above.
- Post-baseline imaging of the brain using the same modality as at baseline should be performed for patients with evidence of CNS disease at baseline and if clinically indicated.
- If consistent with local regulatory guidelines, an initial post-baseline assessment after 4 weeks of treatment (± 7 days) is encouraged. If this scan is performed, the next scan should continue according to the schedule above (beginning at C3D1).
- If consistent with local regulatory guidelines, confirmatory imaging a minimum of 4 weeks (e.g., 28 days) after the first imaging studies that demonstrate a tumor CR or PR by RECIST 1.1 is encouraged. If this scan is performed, the next scan should continue according to the schedule above.

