| | Up to 28 days prior to first dose | D1 ±2 Days | D8 ±2 Days | D15 ±2 Days | D22 ^d ±2 Days | ±2 Days | EOT ^a ≤ 7 days | D 28 ±7 days | |
| Informed Consent ^e | X | | | | | | | | |
| Inclusion/exclusion criteria | X | | | | | | | | |
| Medical, surgical, malignancy history | X | | | | | | | | |
| Molecular Pathology Report(s) describing RET and other alterations ^f | X | | | | | | | | |
| Archived tumor tissue or fresh biopsy ^g | X | | | | | | | | |
| Physical examination and ECOG ^h | X | X | X | X | | D1 C2, 3, 4, 5, etc. | X | X | |
| Vital signs ⁱ | X | X ^j | X ^j | X ^j | | D1 C2, 3, 4, 5, etc. | X | X | |
| 12-lead ECG ^k | X | X | X | | | D1 C2-6 and every 12 weeks | X | X ^l | |
| Urine or serum pregnancy test ^m | X | X | | | | D1 C2, 3, 4, 5, etc. | | | |
| Hematology ⁿ | X | X | X | X | | D1 C2, 3, 4, 5, etc. | X | X | |
| Serum chemistries ^o | X | X | X | X | | D1 C2, 3, 4, 5, etc. | X | X | |
| Liver function tests ^p | | | | | | C2D15 and C3D15 | | | |

| Visit Window | Screening | Cycle 1 | | | | Cycle 2-higher | SFU ^b | | LTFU ^c |
|--|-----------------------------------|---------------|---------------|----------------|-----------------------------|--|------------------------------|-----------------|-------------------|
| | Up to 28 days prior to first dose | D1 ±2 Days | D8 ±2 Days | D15 ±2 Days | D22 ^d ±2 Days | ±2 Days | EOT ^a ≤ 7 days | D 28 ±7 days | |
| Coagulation ^q | X | X | | | | | | | |
| Thyroid panel ^t | X | | | X | | D1 of odd cycles beginning with C3 (C3, 5, 7, etc.) | | | |
| Urinalysis ^s | X | | | X | | D1 C2, and as clinically indicated. | X | X | |
| Calcitonin, CEA (MTC only) ^t | X | X | | X | | D1 C2 and odd-numbered cycles, starting with C3 through C13. Every 12 weeks thereafter (±7 days of each radiologic disease assessment) | X | | |
| Thyroglobulin (non-MTC thyroid cancers only) ^u | X | X | | X | | D1 C2 and odd-numbered cycles, starting with C3 through C13. Every 12 weeks thereafter (±7 days of each radiologic disease assessment) | X | | |
| Blood cortisol, ACTH, 24-hour urine for free cortisol ^v | X | X | | X | | D1 C2 and odd-numbered cycles, starting with C3 through C13. Every 12 weeks thereafter (±7 days of each radiologic disease assessment) | X | | |
| Disease assessment ^w | X | | | | | Perform assessments at week 4 (±7 days, optional) and week 8 (±7 days) and then every 8 weeks (±7 days) until week 48 following C1D1 and then every 12 weeks (±7 days) | X ^x | | X ^y |

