- w. Baseline disease assessment with radiographic tumor measurements using CT or MRI of chest, abdomen, and pelvis; And any other areas with suspected disease involvement within 28 days of C1D1 as clinically indicated. Brain imaging is required at baseline for all RET fusion-positive patients, patients with a history of CNS metastases, or other patients if clinically indicated and subsequent serial scans if brain metastases are present at baseline (MRI preferred, CT with contrast is acceptable if MRI contraindicated). Required only for patients with nonmeasurable bone disease identified at baseline or if clinically indicated. For each modality, IV and oral contrast should be utilized unless there is a clear contraindication (e.g., decreased renal function or allergy that cannot be addressed with standard prophylactic treatments). In the absence of known or suspected disease involvement, head and neck CT/MRI scans are not required for malignancies other than those originating in the head and neck region. Other areas of scanning may also differ depending on disease type. Post-baseline scans should be performed every 8 weeks (± 7 days) until week 48 and every 12 weeks (± 7 days) thereafter, including imaging of the chest, abdomen, and pelvis, using the same modality(ies) as used for baseline imaging assessment until PD, withdrawal of consent, or initiation of a new anticancer therapy(ies). Additionally, any studies performed at baseline that are positive for sites of disease should be repeated at all post-baseline assessments. Additional studies can also be performed as clinically indicated. In addition, Investigators may conduct an initial tumor evaluation on week 4 (± 7 days) and a confirmatory tumor evaluation a minimum of 4 weeks (i.e., 28 days) after the first tumor evaluation that shows a CR or PR by RECIST 1.1, if consistent with local regulatory authority requirements. In addition, an initial post baseline assessment on week 4 (± 7 days) is encouraged if consistent with regulatory guidelines. If a scan is performed on week 4, the next scan should continue according to the schedule above (beginning at week 8). For patients who continue to receive study treatment beyond progression, post PD scans to determine tumor disease assessment should be performed within 8 weeks (± 7 days) of initial PD (PD₁) and every 8 weeks (± 7 days) thereafter until subsequent PD (PD₂), withdrawal of consent, or initiation of a new anticancer therapy(ies). Additional scans can be performed as needed. All scans (including any unscheduled scans performed during the study) will be collected and stored at a central facility to permit central reviewer assessment. Please see the Site Imaging Manual for guidelines on how the various imaging studies should be performed.

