7.4 End of Treatment Visit (All Patients)

Within 7 days of last dose of study drug or at the time of premature discontinuation of treatment, the following procedures will be performed at the EOT visit:

- Scheduling of tumor tissue biopsy from patients who experience PD (optional and if it can be safely performed in the judgement of the Investigator).
- Symptom-directed physical examination, weight, and ECOG.
- Vital signs.
- Resting 12-lead ECG.
- Hematology.
- Serum chemistries.
- Urinalysis.
- Calcitonin, CEA: for patients with MTC only. For each patient, these should be performed in the same laboratory as prior testing to minimize intra-patient variability in measurement.
- Thyroglobulin: for patients with non-MTC thyroid cancer only (unless not measurable due to presence of anti-thyroglobulin antibodies). For each patient, all tests for thyroglobulin should be performed in the same laboratory to minimize intra-patient, lab-to-lab variability in their measurement.
- Blood cortisol, ACTH, 24-hour urine for free cortisol: optional for patients with Cushing's disease related to their cancer.
- Radiographic disease assessment (if not performed within the last 2 cycles). Patients who have an ongoing CR or PR and discontinue study drug for reasons other than PD (e.g., AE, noncompliance, etc.), may (but, for practical reasons and to minimize patient inconvenience, are not required to) have scans collected ~ every 8-12 weeks as outlined above until documented PD.
- Return unused selpercatinib.
- Outpatient diaries for recording daily selpercatinib dosing, H2 blockers, and antacids.
- AEs.
- Concomitant medication(s).
- Patient-reported outcomes:
 - For MTC patients with diarrhea present at baseline: bowel diary.
 - EORTC QLQ-C30.

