6.9.2. Objective Response Rate (ORR)

6.9.2.1. Primary Analysis

ORR is a summary measure of best overall response (BOR) as defined by RECIST Version 1.1. BOR is defined as the best response designation for each patient that is recorded between the date of the first dose of seliperatinib and the date of documented disease progression per RECIST 1.1 or the date of subsequent therapy, whichever occurs first. Each patient's BOR will be categorized as complete response (CR), partial response (PR), stable disease (SD), progressive disease (PD) or not evaluable (NE).

Response (PR or CR) must be confirmed by a repeat assessment performed no less than 28 days after the criteria for response are first met. In the event that the confirmation of a CR or PR occurs at a time point following an NE assessment, the best overall response will be CR or PR. That is, the sequence of time point responses CR-NE-CR (or PR-NE-PR/CR) will be considered a best overall response of CR (or PR). When stable disease is believed to be the best response, it must also meet the minimum interval of 6 weeks (42 days) from the start of study treatment. If

the minimum time is not met when stable disease is otherwise the best time point response, the patient's best response depends on the subsequent assessments. For example, a patient who has stable disease at the first assessment, progressive disease at the second and does not meet minimum duration for stable disease, will have a best response of progressive disease. The same patient lost to follow-up after the first stable disease assessment will be considered inevaluable.

The ORR is defined as the number of patients who achieve a BOR of CR or PR that are confirmed divided by the total number of patients in the analysis population. The point estimate will be accompanied by a 2-sided 95% exact binomial CI using the Clopper-Pearson method.

The primary analysis of ORR is based on the response assessment by the IRC. The efficacy of selpercatinib will be demonstrated primarily on the primary efficacy analysis population. ORR will also be summarized by cohort (1 & 2), as well as by major tumor types across cohorts.

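### The week-8 scan may fall only 14 to 27 days after an encouraged week-4 scan, too soon to confirm a response, and spacing the two by at least 28 days would add no scan

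*Protocol*

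**What the plan says.** **Early scan.** Protocol Section 7.3 says that "an initial post-baseline assessment after 4 weeks of treatment (± 7 days) is encouraged", if local regulatory guidelines allow. Table 7-1 lists it as optional, with the same window.

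**Regular scans.** Section 7.3 schedules these "every 8 weeks (± 7 days) beginning with C3D1 through C13D1". Doing the early scan does not re-time week 8. Section 7.3 says so ("If this scan is performed, the next scan should continue according to the schedule above (beginning at C3D1"), Table 7-1 note w repeats it ("If a scan is performed on week 4, the next scan should continue according to the schedule above (beginning at week 8"), and Appendix G has the same rule.

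**Confirmation.** SAP Section 6.9.2.1 states that a CR or PR "must be confirmed by a repeat assessment performed no less than 28 days after the criteria for response are first met". No tolerance is given, and only confirmed responses enter the primary ORR.

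**Separate confirmatory scan.** The next note in Section 7.3 provides for "confirmatory imaging a minimum of 4 weeks (e.g., 28 days) after the first imaging studies that demonstrate a tumor CR or PR", but only as something encouraged where local guidelines allow. Appendix G says the same. Table 7-1 has a row for this scan without that qualification, while note w makes it a choice for the investigator and note z makes it subject to the regulatory authorities.

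**End of treatment.** Section 7.4 asks for "Radiographic disease assessment (if not performed within the last 2 cycles", and Table 7-1 note x gives the limit as 8 weeks. Neither makes an exception for an unconfirmed response. Imaging after stopping drug without progression is optional.

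**Analysis timing.** Protocol Section 9.4.5 and SAP Section 6.14 allow the primary analysis once all enrolled patients have at least two post-baseline assessments (the SAP excepts early discontinuations). Neither states a minimum spacing between the two.

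**The concern.** The planned distance between the week-4 and week-8 scans equals the minimum confirmation interval exactly, so there is no slack. Each scan has its own window. If week 4 is booked late or week 8 early, the gap falls below 28 days. A patient can then show PR on both scans, both within their windows, and still have no confirmed response.

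The primary endpoint counts only confirmed responses. A patient left in this position who has no later scan showing response is scored as a non-responder because of booking dates, not tumour behaviour. The resulting error in ORR runs downward and depends on how each site books its scans.

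**Working it through.** Neither document gives a figure for this point, so there is none to reproduce. The only plan figures used are from Table 9-1 at n = 20: exact lower limits of 0.41 for an observed ORR of 0.65 and 0.36 for 0.60. Recomputed (Clopper-Pearson), 13/20 gives 40.8% and 12/20 gives 36.1%, in agreement.

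**1. Scan dates (C1D1 = day 1)**

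| Scan | Nominal day | Window |
|---|---|---|
| Week 4 | 29 | 22–36 |
| Week 8 | 57 | 50–64 |
| Week 16 | 113 | 106–120 |

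**2. Gap from week 4 to week 8**

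- Nominal: 57 − 29 = 28 days.
- Shortest: 50 − 36 = 14 days. Longest: 64 − 22 = 42 days.
- Example: week 4 on day 33 and week 8 on day 54 are both in window, but 21 days apart.

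**3. How often the gap is under 28 days.** This happens when the week-8 offset is smaller than the week-4 offset. The documents give no distribution of scan days, so each line below is an assumption.

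| Assumption about scan days | P(gap < 28) |
|---|---|
| Both on the nominal day, or shifted equally | 0% |
| Independent, 90% on the nominal day | 9.5% |
| Independent uniform, week 4 never late (or week 8 never early) | 23% |
| Independent, 50% on the nominal day | 37% |
| Independent, uniform within ±3 days | 43% |
| Independent, triangular within ±7 days | 46% |
| Independent, uniform within ±7 days (105 of 225 pairs) | 47% |
| Independent uniform, week 4 never early | 70% |

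For independent offsets with the same distribution, P = (1 − P(same offset)) / 2. With 15 equally likely days that is (1 − 1/15) / 2 = 46.7%.

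**4. What can still confirm a week-4 response**

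- The confirmatory scan at 28 days or more, if it is done.
- Week 16, which falls 106 − 36 = 70 to 120 − 22 = 98 days after week 4 and so always meets the minimum. SAP Section 6.9.5 accepts an intervening NE or stable assessment.

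**5. Data cutoff.** With a week-4 scan, the two assessments that make a patient ready for the primary analysis can be weeks 4 and 8, which are 14 to 42 days apart. Without it they are weeks 8 and 16, which are 106 − 64 = 42 to 120 − 50 = 70 days apart and always far enough. So the optional scan can make a recently enrolled patient count as sufficiently followed while the response is still unconfirmed.

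**6. Size at n = 20.** Assumptions, none from the documents: 13 responders (65%), half of them first seen at week 4, and 5–15% of the short-gap patients showing no later response.

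- Responders lost = 13 × 0.5 × 0.467 × (0.05 to 0.15) = 0.15 to 0.46.
- Divided by 20: 0.8 to 2.3 percentage points of ORR.
- With the timing share at its extremes: 0 points at 0%, and at most 13 × 0.5 × 0.70 × 0.15 / 20 = 3.4 points at 70%.

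For scale, one whole lost responder is 5 points and moves the lower limit from 40.8% to 36.1%. That is more than twice the 2.3 points above.

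**The case against.** The strongest reply compares with the schedule without the optional scan. The same patient would then be first seen in response at week 8 and confirmed by the confirmatory scan or at week 16. After a short gap, confirmation comes from those same scans. The short gap forfeits an early chance to confirm; it does not usually lose a response that the basic schedule would have counted. This stands, with one exception: at a data cutoff reached on two assessments (step 5), the patient can be worse off than without the week-4 scan. That exception touches only the last patients enrolled, and both documents allow the primary analysis to be updated at a regulator's request.

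Three stronger readings are tempting, and the documents do not support them.

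- *Nearly half of week-4 responders cannot be confirmed.* The 47% is neither a document figure nor an expected rate. It needs independent, uniform scan dates, and it describes only whether week 8 can confirm, not whether the response is ever confirmed.
- *Short-gap responders are scored as stable disease.* Most are delayed rather than lost, because the confirmatory scan and week 16 remain available.
- *Section 7.4 excuses unconfirmed responders from an end-of-treatment scan.* It does so only if a scan was done in the last 2 cycles.

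It is also fair to say that the study is a preliminary assessment without a hypothesis test, that the error is conservative, and that the exact 95% interval at 13/20 (about 41% to 85%) dwarfs it. The Imaging Review Charter cited in SAP Section 6.9.1 and the Site Imaging Manual were not available and may address timing. These points limit the importance of the issue but do not remove the mismatch between the two rules.

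**Conclusion.** The point holds as a scheduling gap with a cheap remedy. The Protocol permits a week-4 to week-8 gap of 14 to 42 days while the SAP needs at least 28. When the gap is shorter, confirmation rests on a scan that is only encouraged, or on week 16. A responder is lost only if neither shows response before progression, new therapy, drug stop or data cutoff.

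The expected effect on ORR is downward and about 1 to 2 points at n = 20. That rests on the assumed scan-date distribution, the assumed half of responders first seen at week 4, and the assumed 5–15% with no later response. Over the full 0–70% timing range, with the other assumptions unchanged, it is 0 to 3.4 points.

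A secondary note concerns Section 7.4 and note x, which have no exception for an unconfirmed response. For example, suppose PR is first seen on day 57 and drug is stopped without progression on day 99. The response is then 42 days old, long enough for confirmation, yet no scan is required because one was done within 8 weeks. The documents do not show how often this would happen, and the main point does not depend on it.

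**What to change.** In Section 7.3, Table 7-1 note w and Appendix G, add: *If a week-4 scan is performed, schedule the week-8 scan within its window and at least 28 days after the week-4 scan.*

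Apply this to every patient with a week-4 scan, not only those whom the site reads as responding. The primary endpoint uses the IRC read, and Section 7.7.2 has scans stored for future independent review. A rule triggered by the site's read would therefore miss responses seen only by the IRC.

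**Feasibility.** The latest week-4 date is day 36, and 36 + 28 = day 64, the last day of the week-8 window. A permitted date therefore always exists, and the chance of a gap under 28 days becomes zero by construction.

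**Cost.** No scan is added and no window is widened. The cost is less booking freedom when week 4 runs late: the week-8 window keeps 15 permitted days if week 4 is 7 days early, 8 if it is on time, and 1 if it is 7 days late.

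**Optional.** For patients who stop drug with an unconfirmed CR or PR at least 28 days old, the sponsor may consider using the confirmatory assessment already listed in Table 7-1. This would add a scan in those patients, and the change above does not depend on it.

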7.4 End of Treatment Visit (All Patients)

Within 7 days of last dose of study drug or at the time of premature discontinuation of treatment, the following procedures will be performed at the EOT visit:

- Scheduling of tumor tissue biopsy from patients who experience PD (optional and if it can be safely performed in the judgement of the Investigator).
- Symptom-directed physical examination, weight, and ECOG.
- Vital signs.
- Resting 12-lead ECG.
- Hematology.
- Serum chemistries.
- Urinalysis.
- Calcitonin, CEA: for patients with MTC only. For each patient, these should be performed in the same laboratory as prior testing to minimize intra-patient variability in measurement.
- Thyroglobulin: for patients with non-MTC thyroid cancer only (unless not measurable due to presence of anti-thyroglobulin antibodies). For each patient, all tests for thyroglobulin should be performed in the same laboratory to minimize intra-patient, lab-to-lab variability in their measurement.
- Blood cortisol, ACTH, 24-hour urine for free cortisol: optional for patients with Cushing's disease related to their cancer.
- Radiographic disease assessment (if not performed within the last 2 cycles). Patients who have an ongoing CR or PR and discontinue study drug for reasons other than PD (e.g., AE, noncompliance, etc.), may (but, for practical reasons and to minimize patient inconvenience, are not required to) have scans collected ~ every 8-12 weeks as outlined above until documented PD.
- Return unused selpercatinib.
- Outpatient diaries for recording daily selpercatinib dosing, H2 blockers, and antacids.
- AEs.
- Concomitant medication(s).
- Patient-reported outcomes:
 - For MTC patients with diarrhea present at baseline: bowel diary.
 - EORTC QLQ-C30.

